### 4 Study design

### 4.1 Overall design

This is an open-label, single arm, two-stage study to evaluate the efficacy and safety of bimiralisib in patients with r/m HNSCC containing *NOTCH1* LOF mutations. The study will be conducted in 1 - 4 centers.

Patients will be treated with 140 mg bimiralisib p.o. once daily on two consecutive days followed by 5 days without treatment in consecutive 7-day treatment blocks. Patients will continue this iterative "2d on / 5d off" treatment scheme until unacceptable toxicity, tumor progression, patient's request for withdrawal, investigator judgment or death, whichever comes first. The bimiralisib dose may be decreased to 100 mg p.o. administered on the same dosing schedule in order to manage safety and/or tolerability (see section on dose interruptions and modifications, section 7.2). Changes in dosing schedule are not allowed.

Stage 1 of the study will enroll 10 patients. Response evaluation of Stage 1 patients will be performed in an ongoing manner (ongoing analysis, OA). If two or more patients in stage 1 show a confirmed partial or confirmed complete response, Stage 2 may enroll 19 patients. Conversely, Stage 2 may not start if only one or no patients in Stage 1 have shown a confirmed partial or confirmed complete response.

If patients withdraw consent or drop out for other reasons unrelated to safety or disease progression, they may be replaced. This includes patients who start smoking (as evidenced by cotinine test) within the first 12 weeks on bimiralisib treatment, because smoking is known to severely compromise bimiralisib exposure due to induction of CYP1A2, the main metabolizing enzyme of bimiralisib. These patients may remain on treatment but will be replaced. Patients for whom IHC analyses indicated high protein levels of NICD which are deemed incompatible with NOTCH1 loss-of-function may be replaced. In total, we anticipate up to 20% of patients to drop out, resulting in enrollment of up to 35 patients in total.

The study will end when all patients have been treated for at least 6 months or have discontinued study participation for any reason, whichever comes first.

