## Table 4: Treatment interruptions and dose reductions for adverse events (except hyperglycaemia) considered related to bimiralisib by the treating physician

Reason	Treatment change
Non-haematological AE Grade 4	Stop bimiralisib treatment permanently.
Haematological AE Grade 4	Interrupt bimiralisib treatment. If AE resolves to baseline or CTCAE grade 1 within 7 days, patients may resume treatment at the reduced dose of 100mg. If AE resolves within 8 to 14 days, patient may resume treatment at the reduced dose of 100mg if agreed between investigator and sponsor. If AE does not resolve to baseline or CTCAE grade 1 within 14 days, bimiralisib treatment must be discontinued permanently.
Grade 3 AE	Interrupt bimiralisib treatment. If AE resolves to baseline or CTCAE grade 1 within 7 days, patient may resume treatment at 140mg. If AE resolves to CTCAE grade 1 within 8 to 14 days, patient may resume treatment at the reduced dose of 100mg. If AE does not resolve to baseline or CTCAE grade 1 within 14 days, bimiralisib treatment must be discontinued permanently.
Any non-haematological AE grade 2	Continue bimiralisib treatment. Dose reduction at the discretion of the treating physician

Patients who after dose interruption do not tolerate bimiralisib treatment at 100 mg must be permanently discontinued. If during the first three months on study, a patient cannot restart at the 100 mg dose level within 14 days, this patient is not evaluable for the primary endpoint, and the investigator must discuss the individual benefit-risk evaluation of this patient with the sponsor before restarting dosing. These patients may be replaced.

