# 9.2.1 Patient demographics and other baseline characteristics

Patient information and material to be collected at screening include:

- Demography (year of birth, sex and race (where permitted)).
- Medical history (e.g. relevant medical and allergic conditions and surgical procedures which could have an impact on the patient's evaluation; this includes the smoking history of a patient) and current medical conditions present at the time of signing informed consent. Ongoing medical conditions, symptoms and disease which are recorded on the Medical History CRF should be graded by NCI-CTCAE version 5.0.
- HNSCC diagnosis (including histology and sites of disease at study entry) determined radiologically according to local practice
- Mutational landscape of the HNSCC: CLIA-certified evidence of a *NOTCH1* LOF mutation; if information on additional mutations is available, this will be collected as well
- All prior antineoplastic treatment regimens including surgical interventions.
- All medications and significant non-drug therapies (including physical therapy, oxygen and blood transfusions) received within 28 days prior to the first administration of bimiralisib
- Physical Examination (Section 9.4.1)
- Vital signs (Section 9.4.2)
- Height, weight
- ECG (Section 9.4.3)
- Laboratory evaluations (e.g. haematology, blood chemistry, HbA1c, cotinine) (Section 9.4.4)
- Patient self-reported mood questionnaires (Section 9.4.5)
- Dermatologic evaluation (Section 9.7.1)
- ctDNA baseline sample collection (Section 9.7.2)
- if available: five unstained sections of most recent available archival tumor material (FFPE, 4um thick, mounted on standard glass slides)
- Pregnancy test (Section 9.4.4)

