# 9.7.3 Assessment of cleaved NOTCH1 protein levels in archival tumor material

If available, archival tumor material (FFPE sections) may be analyzed by immunohistochemistry to assess protein levels of cleaved NOTCH1 protein. Analyses will be performed centrally. Resulting data will be reported separately.

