# 9.11 Patient Replacement

If patients withdraw consent or drop out for other reasons unrelated to safety or disease progression, they may be replaced. This includes patients who start smoking (as evidenced by cotinine test) within the first 12 weeks on bimiralisib treatment. These patients may remain on treatment but will be replaced. Patients who start smoking after the first 12 weeks on bimiralisib treatment will not be replaced. Patients for whom IHC analyses indicate high protein levels of NICD which are deemed incompatible with NOTCH1 loss-of-function may be replaced.

In total, we anticipate up to 20% of patients to drop out, resulting in enrollment of up to 35 patients in total.

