# 10.3.2 Per-protocol set

The per-protocol set (PPS) consists of a subset of the safety set who are compliant with requirements of the clinical study protocol. All protocol deviations or conditions leading to exclusion from the PPS will be detailed in the data handling plan and statistical analysis plan.

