# **10.4.1** Efficacy analyses

All efficacy analyses will be performed on the PPS.

ORR including confirmed complete response (CR), and confirmed partial response (PR) is the primary endpoint.

Frequency and percentage of the ORR with a two-sided 95%-confidence interval will be determined.

Secondary endpoints include additional clinical efficacy assessment by time to response (TTR), duration of response (DOR), time to treatment failure (TTF) and progression-free survival (PFS).

Time to event data will be summarized using the Kaplan-Meier methodology.

Time to response (TTR) is defined as the time from first study drug administration to the first documentation of response (complete or partial).

Duration of response (DOR) is defined as the time from the date of the first confirmed response to the first documentation of disease progression, whichever occurs first

Progression- free survival (PFS) is defined as the time from first study drug administration to disease progression or death due to any cause.

Time to treatment failure (TTF) is defined as the time from first study drug administration to any treatment failure including disease progression or discontinuation of treatment for any reason (e.g., disease progression, AE, patient withdrawal of consent, initiation of new treatment without documented progression, death)

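### NICD-based replacement is discretionary and not shielded from response: if replaced patients leave the 29 and non-responders are replaced more often than responders, type I error exceeds the design's exact 4.7%

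*Protocol*

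**What the plan says.** Protocol 9.11 provides: "Patients for whom IHC analyses indicate high protein levels of NICD which are deemed incompatible with NOTCH1 loss-of-function may be replaced". Section 4.1 has the same rule in near-identical words. Neither section limits it to patients who have not yet been dosed.

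The tissue is requested at screening, if it exists: "five unstained sections of most recent available archival tumor material" (9.2.1). Nothing holds dosing for a result. The assay is optional: "archival tumor material (FFPE sections) may be analyzed by immunohistochemistry to assess protein levels of cleaved NOTCH1 protein" (9.7.3). The same section says the work is central, but not that the reader is kept unaware of outcome. It gives no scoring rule, threshold or turnaround time.

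Section 9.11 opens with a general limit: "If patients withdraw consent or drop out for other reasons unrelated to safety or disease progression, they may be replaced". The NICD sentence comes later in that paragraph, and the text does not say whether the limit governs it. The smoking route in the same paragraph has an objective test (cotinine) and a 12-week cut-off; the NICD route has no counterpart to either.

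On the denominator, section 7.2 says of one other replaceable group (patients unable to restart at the reduced dose in time) that "this patient is not evaluable for the primary endpoint". No such statement is made for NICD. Section 10.4.1 says: "All efficacy analyses will be performed on the PPS". Section 10.3.2 says: "All protocol deviations or conditions leading to exclusion from the PPS will be detailed in the data handling plan and statistical analysis plan". The supplied SAP text consists of the hypotheses and sample-size subsections and contains no such list.

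**The concern.** A Simon design keeps its error rate if whether a patient counts towards the 10 and the 29 does not depend on whether that patient responded. Here two discretionary steps (stain or not, replace or not) can both be taken after response is known. Stage 1 response is evaluated continuously (4.1), and the principal investigator and sponsor representatives review tumour response at least every two months (12.1.8).

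A patient without a response could therefore have archival slides stained, be judged NICD-high and be replaced, while a responder's slides are never stained. If the replaced patient then drops out of the 29, the count of 6 becomes easier to reach under the null and the PPS response rate is biased upward. The safety-set count and the review minutes would show that patients had been replaced. However, the supplied text plans no response rate in all treated patients, so the effect on the primary result would not be visible.

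**Working it through.** **Inputs.** Protocol 10.1-10.2 and SAP 1.1-1.2: null ORR 10%, target 30%, one-sided alpha 0.05, power 80%; stage 1 n = 10, continue if at least 2 respond; total 29, reject if at least 6 respond. Enrolment is up to 35, so at most 35 - 29 = 6 replacements for all reasons together. The documents give no NICD-high rate, so all replacement rates below are assumptions.

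**1. The plan's own design.** P(reject) = sum over x = 2 to 10 of P[Bin(10, p) = x] × P[Bin(19, p) ≥ 6 - x]. At p = 0.10:

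| Stage 1 responses x | P(x) | P(stage 2 ≥ 6 - x) | Product |
|---|---|---|---|
| 2 | 0.1937 | 0.1150 | 0.0223 |
| 3 | 0.0574 | 0.2946 | 0.0169 |
| 4 | 0.0112 | 0.5797 | 0.0065 |
| 5 | 0.0015 | 0.8649 | 0.0013 |
| 6 or more | 0.0001 | 1 | 0.0001 |

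The sum is 0.0471. At p = 0.30 the same formula gives 0.8051. The stated design is reproduced, with about 0.3 points between its exact level and the 5% limit.

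**2. Unequal replacement rates.** Let qN and qR be the chances that a non-responder and a responder are replaced and leave the 29. Without a cap on replacements, a counted patient responds with probability p(1 - qR) / [p(1 - qR) + (1 - p)(1 - qN)]. For qN = 5%, qR = 2.5% this is 0.0975 / (0.0975 + 0.855) = 0.1024. For 10% v 0% it is 0.10 / (0.10 + 0.81) = 0.1099. For 5% v 10% it is 0.09 / (0.09 + 0.855) = 0.0952. An exact recursion over the 29 places, allowing at most six replacements, gives:

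| Non-responders v responders replaced | Type I error at true ORR 10% |
|---|---|
| Equal (5% or 10% in both) | 4.7% |
| 5% v 2.5% | 5.2% |
| 10% v 7.5% | 5.2% |
| 10% v 5% | 5.7% |
| 10% v 0% | 6.8% |
| 5% v 10% (reverse) | 3.9% |

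**3. A fixed number of non-responders replaced because of non-response.**

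- One, used only after stage 1: it matters when the trial has continued and ends on exactly 5 responses (probability 0.0545) and the replacement responds (0.10). Type I error is 0.0471 + 0.0055 = 0.0525 (unrounded), or 5.3%.
- One, available from stage 1: it can also turn 1 of 10 into 2 of 10. That adds 0.3874 × 0.10 × 0.1150 = 0.0045, giving 0.0570, or 5.7%.
- Three: 6.4-7.9%.
- Six: 8.2-11.8%. This spends the entire allowance on NICD-labelled non-responders and is an extreme.

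**4. What an all-treated rate would show.** 6/29 is 20.7% (Clopper-Pearson 95% CI 8.0-39.7%). With three replaced non-responders counted, 6/32 is 18.8% (7.2-36.4%).

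**The case against.** The strongest reply is that the harm is doubly conditional. It needs replaced patients to leave the 29 and non-responders to be replaced preferentially, and the documents state neither. The reverse imbalance lowers type I error. PPS exclusions are deferred to a data handling plan that was not supplied and to an SAP of which only two subsections were. All of this stands, and it limits the claim.

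There are also mitigations. NOTCH1 loss of function is already confirmed centrally at entry (inclusion criterion 3). Staining is possible only where archival tissue exists, and it is read centrally. The periodic review includes a physician not directly involved in the trial's conduct. These may keep NICD replacements few, but none of them blinds the decision to response. If the general limit in 9.11 also governs the NICD route, a patient who leaves because of progression could not be replaced on this ground and the scope for inflation is smaller. It would not vanish, because a patient with stable disease is also a non-responder.

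A reader might infer that the rule will be used to remove treatment failures, or that type I error is inflated as planned. The documents support neither inference: they show only that nothing supplied prevents outcome-dependent removal. Nor is excluding NICD-high patients wrong in itself. Done independently of response, it leaves type I error at 4.7%.

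**Conclusion.** The point holds in conditional form. Removal from the 29 is the natural reading, since the decision rule is fixed at 29 while enrolment may reach 35, but the supplied text does not say so. Given removal, any excess of replaced non-responders over responders raises type I error above 4.7%. Even mild imbalance, or one replacement prompted by non-response, passes the 5% limit; plausible partial selection gives about 5.2-6.8%. The figures for six replacements should not be read as an expected size. Every rate used is an assumption. Confidence is medium because the full SAP or data handling plan may settle both the denominator and the timing. The change is worth making because the primary decision rule is exposed and protection costs little.

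**What to change.** (a) In Protocol 4.1, 9.7.3 and 9.11:

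- have the sponsor pre-specify the NICD cut-off;
- stain every patient with available archival tissue, so that testing itself cannot be selective;
- allow NICD replacement only on a central reading made blind to outcome and recorded before the patient's first on-treatment tumour assessment and before any documented progression. That assessment may be the Day 43 scan or an earlier end-of-treatment scan, so a Day 43 deadline alone is not enough;
- apply the rule to every patient who meets the cut-off;
- keep patients with later results in the primary denominator;
- state whether a patient replaced under the rule leaves the 29, and whether the general limit on replacement in 9.11 applies to this route.

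(b) In 10.4.1, report ORR with its 95% CI in all treated patients, including those replaced for any reason, beside the PPS result. List each replacement with its reason, its date and the response known at that time.

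**Cost.** Protocol wording, earlier and complete staining of slides already requested at screening, one table and one listing. It also requires a workable cut-off and a central turnaround ahead of the first scan; the documents give no assay information on either. The statistical price is that late-identified NICD-high patients stay in the denominator. If they respond at 10% rather than 30% (assumption), power falls from 80.5% to 77-80% with one such patient, 73-79% with two and 69-78% with three. The low end applies if all are in stage 1, the high end if all are in stage 2.

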# 9.12 Follow up period

# 9.12.1 Safety follow-up

All patients will be followed up for safety up to 30 days after last dose of PQR309. The end of this period is defined as the "end of study" (EOS). At EOS, the investigator should contact the patient to inquire about any AE observed/concomitant medication taken during this period. This maybe done via a phone call. Patients whose treatment is interrupted or permanently discontinued due to an adverse event, including abnormal laboratory value, must be followed until resolution or stabilization of the event, whichever comes first. This will include all study assessments appropriate to monitor the event.

# 9.12.2 Loss to follow-up

Patients lost to follow up should be recorded as such on the CRF. For patients who are lost to follow-up, the investigator should show "due diligence" by documenting in the source documents steps taken to contact the patient, e.g., dates of telephone calls, etc.

# **10** Statistical considerations

The data will be analyzed by PIQUR and/or a designated CRO. Any data analysis carried out independently by an investigator should be submitted to PIQUR before publication or presentation. The data from all centers that participate in this study will be combined in the final safety and efficacy analysis.

# **10.1** Statistical hypotheses

This is an open-label, single arm, two-stage study evaluating clinical efficacy, safety and pharmacokinetics of bimiralisib in patients with recurrent or metastatic HNSCC harboring *NOTCH1* LOF mutations. The primary goal of the clinical trial is to determine the objective response rate (ORR, including confirmed complete and partial responses) in patients with r/m HNSCC harboring *NOTCH1* to oral bimiralisib. An ORR of 10% or less is considered to be uninteresting and therefore this study has been designed with a reasonable power to detect a response rate of 30%.

# **10.2** Sample size determination

To minimize accrual if bimiralisib is ineffective, a Simon's optimal two-stage design is used. In order to have 80% power to detect a response rate of 30%, (one-sided  $\alpha$ =0.05 and  $\beta$ =0.20) up to 10 patients will be enrolled in the first stage. If 1 or 0 patient respond to the treatment, the trial will be closed due to futility and the treatment is considered ineffective. If two or more patients have an objective response, the study will enroll an additional 19 patients in the second stage. The null hypothesis (H0: ORR  $\leq$  10%) will be rejected if the number of responses is  $\geq$  6 in 29 patients.

If patients withdraw consent or drop out for other reasons unrelated to safety or disease progression, they may be replaced (see section 9.11). We anticipate up to 20% of patients to drop out, resulting in enrollment of up to 35 patients in total.

This sample size is also reasonable to evaluate the pharmacokinetic and other correlative science endpoints; yet, no explicit sample size justification is made for these exploratory endpoints.

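### Does a ceiling of 35 patients fall short of the 29 in the decision rule if 20% drop out?

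*Protocol*

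**What the plan says.** Protocol 10.2 describes a Simon optimal two-stage design. For stage 1, "up to 10 patients will be enrolled in the first stage". The futility rule reads: "If 1 or 0 patient respond to the treatment, the trial will be closed due to futility". Otherwise "the study will enroll an additional 19 patients in the second stage". The null hypothesis is rejected at or above "6 in 29 patients". The rates behind the design are a null of 10% (section 10.1: "An ORR of 10% or less is considered to be uninteresting") and an alternative of 30% ("In order to have 80% power to detect a response rate of 30"%), with one-sided alpha 0.05.

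The next paragraph allows replacement of patients who leave for reasons other than safety or progression, and ends: "We anticipate up to 20% of patients to drop out, resulting in enrollment of up to 35 patients in total". SAP 1.2 repeats this. Section 4.1 has it as "In total, we anticipate up to 20% of patients to drop out, resulting in enrollment of up to 35 patients in total", and section 9.11, on patient replacement, closes with the same sentence. Sections 4.1 and 9.11 also name two further routes to replacement: starting to smoke in the first 12 weeks, and NICD protein levels judged incompatible with loss of function.

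**The concern.** The usual way to allow for drop-out is to divide the required number by one minus the drop-out rate. Here that gives 37, while the plan gives 35, which is what multiplying 29 by 1.20 produces. That looks like a familiar slip.

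The sentence also puts the 20% next to the 35 enrolled, so it is easy to read it as a share of everyone enrolled. On that reading 28 patients remain, and the final rule is written only for 29. The design has little power to spare: it exceeds 80% by about half a point. A shortfall of even one patient would take it below the stated target, and the documents give no rule for a final count other than 29.

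**Working it through.** **Inputs.** Stage 1 size 10, stage 2 size 19, stop at 1 or fewer responses in stage 1, reject at 6 or more in total, drop-out up to 20%, enrolment up to 35 (Protocol 10.2 and SAP 1.2); null rate 10% and alternative 30% (Protocol 10.1 and SAP 1.1).

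**1. The underlying design.** With stage sizes n1 and n2, the probability of rejecting at true rate p is the sum over x = 2 to n1 of P(Bin(n1, p) = x) × P(Bin(n2, p) ≥ 6 − x).

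- 10+19, p = 0.10: 0.0471 (type I error)
- 10+19, p = 0.30: 0.8051 (power)

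Both meet the stated 0.05 and 80%.

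**2. The plan's 35.** 20% of the planned 29 is 5.8, so 6 replacements; 29 + 6 = 35. Equivalently, 29 × 1.20 = 34.8, rounded up to 35. The stated figure reproduces exactly, provided no replacement needs replacing in turn.

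**3. The other reading.** If 20% is a share of all enrolled:

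- 35 × 0.80 = 28.0
- 36 × 0.80 = 28.8
- 37 × 0.80 = 29.6

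So 37 would be needed for an expected 29 (29/0.80 = 36.25). Letting replacements drop out at 20% as well gives the same answer: expected losses of 29 × 0.20/(1 − 0.20) = 7.25, so 8, and 29 + 8 = 37. With 35 enrolled, 29 remain as long as no more than 6 are lost, which is 6/35 = 17.1% of enrolled or 6/29 = 20.7% of planned.

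**4. What one patient fewer costs.** The missing patient would be in stage 2, because a total of 35 cannot run out while the first 10 places are being filled. The formula in step 1 with n2 = 18 and the cut-off still at 6:

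| Stage sizes | Type I error (p = 0.10) | Power (p = 0.30) |
|---|---|---|
| 10+19 | 0.0471 | 0.8051 |
| 10+18 | 0.0418 | 0.7933 |

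Power changes by 0.8051 − 0.7933 = 0.0118, about 1.2 percentage points. Type I error falls.

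**5. When it could happen.** Four things must coincide: stage 2 opens (probability 1 − 0.1493 = 0.851 at a 30% response rate and 1 − 0.7361 = 0.264 at 10%), drop-out reaches its stated upper limit, that limit refers to all enrolled, and 35 is treated as a hard ceiling.

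**The case for a change.** The strongest case for a change is that replacements are ordinary trial patients and nothing exempts them from dropping out. The routes to replacement go beyond withdrawal of consent: early smokers, incompatible NICD levels and, under section 7.2, certain patients who cannot restart dosing in time and are then not evaluable for the primary endpoint. Efficacy is analysed in the per-protocol set (section 10.4.1), so the gap between enrolled and evaluable matters. If each of exactly 35 patients dropped out independently at 20% (an assumption), the chance of keeping at least 29 would be only 0.433; with 37 enrolled it would be 0.686.

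What stands is that the denominator is not stated and that the same silence recurs in four places. The rest carries less weight:

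- The independence calculation fixes enrolment in advance. In a replacement design, enrolment responds to losses as they occur.
- Both the 20% and the 35 are given as anticipated upper limits. They forecast accrual; the decision rule is set separately.
- A stage 1 of only 9 evaluable patients would cost more (9+19: power 75.4%, type I error 0.038). It would have to come from something else, such as a choice not to replace or a later exclusion from the per-protocol set. The synopsis ties the formal futility analysis to assessment of all 10 stage 1 patients.
- Spelling out that 35 covers 6 replacements would not make 29 any more likely. Raising the figure to 37 would add up to two patients to protect about 1.2 points of power, and only on a reading that the text does not require.

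**Conclusion.** No change follows. This is a missing detail that readers can fill from context: the planned 29 plus about 6 replacements is 35. The conclusion rests on reading the 20% as a share of the planned 29, with no replacement itself replaced. The placement of the sentence within the replacement provisions supports that reading, though no section states it.

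If the assumption fails at the full 20%, the trial ends with 28 patients. Keeping the cut-off of 6 responses is then the sensible course for the analyst: type I error is 0.042, below the 0.05 allowed, and power is 79.3% against 80.5% as planned. The departure is conservative and about one percentage point in size. No stated figure, threshold or conclusion of the trial depends on settling the denominator.
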